11.1 Adverse Events

All reported AEs will be coded and summarized by system organ class (SOC) and preferred term (PT) according to Medical Dictionary for Regulatory Activities (MedDRA). The investigator verbatim term and SOC/PT will be shown simultaneously on the data listings of all AEs.

AEs will be classified as TEAEs or non-TEAEs depending on the comparison of AE onset date/time with the study treatment start date/time, and they will be summarized separately. A TEAE is an AE with an onset at or after the start of study treatment, otherwise it is a non-TEAE.

AE causality will be classified and assessed by the investigator. If the causality is definitive, probable, possible, or doubtful/unlikely, the event will be defined as a suspected adverse drug reaction (ADR). If the causal relationship is labeled as “Unrelated”, it will be considered that the AE is not imputable to the investigational medicinal product and it is not a suspected ADR. In the framework of this study, a suspected ADR with a causal relationship of “definite” is named as adverse reaction (AR).

The incidence of non-TEAEs will be summarized. An overall summary of TEAEs, incidences of TEAEs, suspected ADRs, ARs, TEAEs with outcome of deaths, TEAEs leading to premature discontinuation from the study will be provided. The summary of treatment emergent bleeding events will be provided through the follow-up period (i.e., all treatment emergent bleeding events recorded), through 1 week post surgery (Day 7), and through 2 weeks post surgery (Day 14). Incidences of TEAEs will also be summarized by seriousness, severity, and causal-relationship to the study drug. Each subject is only counted once at each level of SOC and PT. For the summary by severity or by causality, each subject is only counted once per SOC or PT using the most severe or highest causality event. Summary tables will be sorted alphabetically by SOC and PT.

All AEs, deaths, SAEs, AEs leading to premature discontinuation from the study will be listed separately.

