4.3.2 Causality of Adverse Event

The investigator will be asked to assess the causal relationship of the AE to the study treatments according to the following classification based on Karch FE et al (42):

- **Definite:** An event that follows a reasonable temporal sequence from administration of the treatment or in which the treatment level has been established in body fluids or tissues; that follows a known response pattern to the suspected treatment; and that is confirmed by improvement on stopping the treatment (dechallenge), and reappearance of the event on repeated exposure (rechallenge).
- **Probable:** An event that follows a reasonable temporal sequence from administration of the treatment; that follows a known response pattern to the suspected treatment; that is confirmed by dechallenge; and that could not be reasonably explained by the known characteristics of the subject's clinical state.
- **Possible:** An event that follows a reasonable temporal sequence from administration of the treatment; that follows a known response pattern to the suspected treatment; but that could have been produced by the subject's clinical state or other modes of therapy administered to the subject.
- **Doubtful/Unlikely:** An event that follows a reasonable temporal sequence from administration of the treatment; that does not follow a known response pattern to the suspected treatment; but that could not be reasonably explained by the known characteristics of the subject's clinical state.
- **Unrelated:** Any event that does not meet the criteria above.

The operational tool to decide the AE causal relationship is based on algorithms by Karch-Lasagna and Naranjo (43, 44).

When an AE is classified, assessing causal relationship by the investigator, as definitive, probable, possible, or doubtful/unlikely, the event will be defined as suspected ADR. When the causal relationship is labeled "Unrelated", then it will be considered that the AE is not imputable to the study treatment and it is not a suspected ADR. For definition of AR, see [Section 4.3.3](#).

Any AE experienced by the subject prior to the first blinded investigational product infusion on Day 0 will be labeled as Unrelated to the study drug.

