4.3.7 Adverse Event Documentation

All AEs and SAEs occurring after the subject has signed the **informed consent form (ICF)** must be fully recorded in the subject’s eCRF or SAE form. For example, a laboratory test abnormality considered clinically relevant, eg, causing the subject to withdraw from the study, requiring treatment, causing apparent clinical manifestations, or judged relevant by the investigator, should be reported as an AE. Each event must be adequately supported by documentation as it appears in the subject’s medical or case file.

At each visit, AEs will be elicited by asking the individual a non-leading question such as “Do you feel different in way since the last visit?”. Moreover, AE will also be collected through directly observed events or spontaneously volunteered by the subject. Clearly related signs, symptoms, and abnormal diagnostic procedures should preferably be grouped together and recorded as a single diagnosis or syndrome wherever possible. It is responsibility of the Investigator to ensure that AEs are appropriately recorded.

The following variables must to be recorded on the AE eCRF entry:

1. the verbatim term (a diagnosis is preferred)
2. date/time of onset
3. date/time of resolution
4. intensity (mild, moderate, severe)
5. causality (unrelated, doubtful/unlikely, possible, probable, definite)*
6. seriousness (yes, no)
7. action taken (with regard to study drug)
8. other action (to treat the event)
9. outcome and sequel (follow-up on AE)

*Causality assessment will be only made when the AE occurs after the subject has received one or another study treatment. AE occurring before subject's exposure to study treatments will be always labeled as "Unrelated".

For AEs that occur during infusions, the infusion rate in effect at the time of onset of the AE, the time of onset of the AE and the time of AE change materially in intensity and/or resolve will be captured the eCRF entry.

In addition to the Investigator's own description of the AEs, each AE will be encoded by the sponsor (or designee, eg, CRO) according to the MedDRA® dictionary of medical codes.

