5.1.1 Adverse Events

Treatment emergent adverse events (TEAEs) will be characterized based on AE onset date/time relative to each subject’s study treatment start date/time.

Adverse events with incomplete start dates will be considered TEAEs if:

- Day and month are missing and the year is equal to or after the year of study treatment start date;
- Day is missing, month is present and the year is after the year of study treatment start date;
- Day is missing and the year is equal to the year of study treatment start date and the month is equal to or after the month of study treatment start date;

- Day, month, and year are all missing.

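### The TEAE rule looks only at onset, so an event present at dosing that worsens after study drug is left out of the TEAE and treatment-emergent bleeding tables

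*SAP*

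**What the plan says.** SAP 11.1 gives the definition: "A TEAE is an AE with an onset at or after the start of study treatment, otherwise it is a non-TEAE". The derivation rule in SAP 5.1.1 is consistent with it: "Treatment emergent adverse events (TEAEs) will be characterized based on AE onset date/time relative to each" subject's start of treatment. Neither section has a clause for worsening.

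SAP 11.1 summarizes the incidence of non-TEAEs. For TEAEs it plans much more: an overall summary, incidence tables by seriousness, severity and causality, a table of TEAEs with fatal outcome, and one of TEAEs leading to discontinuation. For bleeding, "The summary of treatment emergent bleeding events will be provided through the follow-up period", with further cuts at Day 7 and Day 14. SAP 11 presents all safety analyses by treatment on the safety population.

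On causality, Protocol 4.3.2 states: "Any AE experienced by the subject prior to the first blinded investigational product infusion on Day 0 will be labeled as Unrelated". Protocol 4.3.7 repeats it: an AE arising before the subject's "exposure to study treatments will be always labeled as" Unrelated.

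**The concern.** AE collection opens at consent, and study drug is given once, immediately after induction of anesthesia. Some subjects can therefore have an unresolved event when the infusion starts. Aggravation of such an event is one form that drug harm can take. Bleeding is the harm that the Protocol itself raises about antithrombin supplementation (Protocol 1.1 and 1.2), and bleeding risk is a stated safety objective (Protocol 2.3).

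A bleed that is mild before dosing and severe afterwards would not be counted in the tables built to compare severity, seriousness, death and bleeding between arms. A fatal case would also leave two death counts to reconcile: it would enter all-cause mortality but not the table of TEAEs with fatal outcome.

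Elsewhere the plan does treat worsening as relevant. SAP 11.4 tabulates whether existing examination findings worsened, and in Protocol 4.3.5 the SAE exemption for pre-planned hospitalization depends on the condition not having worsened from baseline.

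**Working it through.** The question is one of definition, and no figure in the plan has to be reproduced. The check sets the rules side by side and applies them.

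**Inputs**

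- Collection window: from signed consent to the Day 30±4 visit (Protocol 4.2.1 and 4.3.1). Screening falls within two weeks before surgery (Protocol 3.6.1).
- Dosing: a single dose directly after induction (Protocol 3.3.2.1). The pre-dose window is therefore about two weeks at most.
- Classification: onset date/time against treatment start (SAP 5.1.1 and 11.1).
- Record of worsening: Protocol 4.3.7 lists onset, resolution, intensity, seriousness and outcome for each AE. It asks for the time of a material change in intensity only for AEs that occur during infusions. Neither document tells sites to open a new record when an AE worsens.

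**Applying the rule**

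| Event | SAP rule (onset only) | Onset-or-worsening rule |
|---|---|---|
| Onset before dosing, worsens after | non-TEAE | TEAE |
| Onset before dosing, does not worsen | non-TEAE | non-TEAE |
| Onset at or after dosing | TEAE | TEAE |

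Only the first type changes class.

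**Where an event of the first type is reported under the current plan**

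- Absent: the TEAE tables by severity, seriousness and causality, the fatal-outcome and discontinuation tables, and the bleeding summaries through follow-up, Day 7 and Day 14.
- Present: the by-treatment non-TEAE incidence summary, for which no breakdown by severity, outcome or bleeding window is specified, and the listings of AEs, deaths and SAEs.
- Independent of the TEAE flag: chest-drain loss, transfusion, reexploration and all-cause mortality (SAP 10.2), the primary composite (SAP 10.1), and laboratory and vital-sign changes from baseline (SAP 11.2 and 11.3).

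**Exceptions**

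- Some incomplete start dates default to TEAE. One case is "Day is missing and the year is equal to the year of study treatment start date and the month is equal to or after" that of dosing; a wholly missing date is another (SAP 5.1.1).
- A worsened laboratory, vital-sign or examination finding may be reported as an AE in its own right (SAP 11.2 to 11.4) and would then have its own, later onset. The documents allow this but do not ensure it.

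**Suspected ADRs.** These are defined by causality, not by the TEAE flag. A pre-dose event cannot be one, because the Protocol fixes its causality as Unrelated. This gap would remain if only the SAP definition were changed.

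**The case against.** The strongest reply is that little is lost. Surgical and bypass bleeding starts after dosing and is a TEAE in any case. The main bleeding comparisons (chest-drain loss, transfusion, reexploration) ignore the TEAE flag, as do mortality and the laboratory and vital-sign tables. The affected events still appear by arm in the non-TEAE summary. All of this stands and limits the importance of the point. It does not remove it: the AE bleeding summary covers any site through the whole follow-up, and the non-TEAE summary does not show that an event became worse.

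Three stronger readings are tempting, and the documents do not support them.

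- *The rule can only hide harm.* It applies equally to both blinded arms. If pre-dose events worsened more often on placebo, it would hide a benefit.
- *The SAP sentence causes the gap in the suspected-ADR tables.* The Protocol's labeling rule causes it.
- *A definite number of subjects is misclassified.* Suppose that 10–20% of 202 subjects per arm have an event ongoing at dosing and that 5–10% of these worsen. That gives 202 × 0.10 × 0.05 = 1.0 to 202 × 0.20 × 0.10 = 4.0 subjects per arm. Both percentages are pure assumption. The 202 is the number to be randomized, whereas the tables use dosed subjects, and SAP 13 says that more subjects than expected went undosed. A total over all event types also cannot be set against the expected count of one rare outcome.

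It can also be said that eCRF completion instructions, which are not among the documents, may tell sites how to record worsening. That is possible, but the SAP rule would use such information only if it produced a new record with a new onset.

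**Conclusion.** The point holds as a defect of definition with limited consequences. An AE that starts between consent and dosing and then worsens, becomes serious or becomes fatal after study drug is counted as a non-TEAE. Apart from the narrow exceptions, it is missing from the TEAE severity, seriousness, causality and fatal-outcome tables and from the treatment-emergent bleeding summaries.

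The effect is probably small, because the window is short and many of the serious consequences are captured elsewhere. Its size cannot be estimated from the documents, and its direction is not fixed. What can be said is that any excess of worsening under AT-III would be missed in these particular tables.

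This rests on one assumption: that a worsening event keeps its single pre-dose onset. That is how the documents read in the absence of a new-record rule.

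**What to change.** In SAP 5.1.1 and 11.1, define a TEAE as an AE that either starts at or after the start of study treatment, or starts earlier and increases in severity, becomes serious or becomes fatal at or after that time.

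Before unblinding, review the AEs that began before dosing and had not resolved by then. Use only data already recorded: the AE entry, the SAE form, the date of death and the intensity-change time where it was captured. That last item may help little, since an event that begins during the infusion is already a TEAE. For the Day 7 and Day 14 bleeding summaries, use the date of worsening where one is available, and flag the events where it is not.

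Separately, say in the safety report that Protocol 4.3.2 and 4.3.7 label pre-dose events Unrelated. Their absence from the suspected-ADR tables, and their Unrelated entry in the TEAE causality table once reclassified, then reads as the result of a rule and not of a causality assessment. This needs no Protocol change.

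The cost is a change of SAP wording, a small blinded review, and a few more events in the TEAE tables of both arms. The primary analysis is unaffected, and no new data are collected.

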11.2 Clinical Laboratory Evaluations

All clinical laboratory test results will be listed.

The absolute values and change from baseline will be summarized using descriptive statistics by parameter and visit. Shift tables, based on the low/normal/high flags, will also be summarized by parameter and visit. Laboratory results out of the normal range judged by the investigators as clinically relevant will be reported, analyzed, and discussed as AEs.

11.3 Vital Signs

All vital sign data for systolic blood pressure, diastolic blood pressure, heart rate, temperature, and respiratory rate will be listed.

The absolute values and change from baseline will be summarized using descriptive statistics by visit.

Abnormal vital signs judged by the investigators as clinically significant will be reported, analyzed, and discussed as AEs.

11.4 Physical Examinations

All physical examination data will be listed by subject.

Findings at the Screening Visit will be summarized with numbers and percentages by body system. Entries for 'Other' body systems will be grouped together; a subject with 2 or more 'Other' entries will be counted only once. Physical exam change findings after the Screening Visit will be summarized with numbers and percentages for each response category to the question 'Were there any new findings or existing findings that worsened?' ('No', 'Yes').

Abnormal findings judged by the investigators as clinically significant will be reported, analyzed, and discussed as AEs.

12 Interim Analysis

No interim analysis is planned.

13 Changes in Planned Analysis

Modified ITT (mITT) is added as a new analysis population and will be used for efficacy analyses that were planned to be conducted on ITT. The reason of this change is that the number of subjects who were randomized but not administered study drug is more than expected and the efficacy variables are complications and sequelae of complex cardiac surgery. Only subjects who are dosed and operated on should be evaluated.

Per protocol (PP) population will be based on mITT, not just ITT as originally planned.

Safety population will be used for demographic and baseline summary analyses which were planned to be conducted on ITT population. The reason of this change is that the number of subjects who were randomized but not administered study drug is more than expected.
